5.7. Tertiary/Exploratory Endpoint(s) Analysis

The following exploratory endpoints will be analyzed using the FAS without adjustment for multiplicity.

Proportion of participants requiring mechanical ventilation after study entry

The frequency and proportion of participants will be reported by treatment group. The difference between treatment groups will be compared using a Cochran-Mantel-Haenszel (CMH) test stratified by Country (USA, Brazil), age (≤ 65 vs > 65), corticosteroid use (yes vs no) and remdesivir strata (yes, no). The common risk difference and two-sided 95% stratified Newcombe confidence interval will be reported. The strata will be weighted using Mantel-Haenszel weights.

Change from baseline in SARS-CoV-2 viral load at Days 10/EOT, 14, 21 and 28

The change from baseline to each of days 5, 10, 14, 21 and 28 in the SARS-CoV-2 viral load will be derived by taking the SARS-CoV-2 viral load at the post baseline timepoint (i.e., Days 10, 14, 21 and 28) and subtracting the baseline SARS-CoV-2 viral load. Participants who are discharged prior to day 10, will have their end of treatment assessment, mapped to day 10. Missing data will be assumed to be missing at random and this endpoint will be analyzed using likelihood-based methods, therefore missing data will be maintained as missing. The change from baseline to each of days 5, 10, 14, 21 and 28 in the SARS-CoV-2 viral load will be

analyzed using a mixed model for repeated measures (MMRM) approach as outlined for the co-primary endpoint of change from baseline in SpO₂/FiO₂ ratio. The data may be log transformed prior to analysis if the assumptions of normality are violated. For values below the limit of quantification, half the value between 0 and the limit of quantification will be used. This analysis will only be conducted for patients who are positive at baseline based on PCR testing.

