8.1.2. Measure of Clinical Support

At each study day while hospitalized, the following measure of clinical support should be assessed:

- Oxygen requirement
- Non-invasive mechanical ventilation (via mask)
- Mechanical ventilator requirement (via endotracheal tube or tracheostomy tube) or Extracorporeal membrane oxygenation (ECMO) requirement
- Level of consciousness: alert vs. (arousable only to voice or pain or unresponsive)

In addition, date of hospital discharge readiness or date of hospital discharge (if different) will be collected.

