8.1.3. Clinical Status Ordinal Score

Clinical status will be assessed using the 6-point ordinal score (Table 5). The ordinal scale is an assessment of the clinical status at the first assessment of a given study day. Each day, the worse score for the previous day will be recorded. i.e. on day 3, day 2 score is obtained and recorded as day 2. This scale has been used successfully as an endpoint for evaluation of treatments for severe influenza requiring hospitalization (Peterson, 2017).

Table 5: A 6-Point Ordinal Score for Assessing Clinical Status

Score	Description
1	Not hospitalized
2	Hospitalized, not requiring supplemental oxygen
3	Hospitalized, requiring supplemental oxygen
4	Hospitalized, on non-invasive ventilation or high flow oxygen devices
5	Hospitalized, on invasive mechanical ventilation or ECMO
6	Death

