5.1. General Considerations

The following is a list of general reporting conventions:

- Percentages will be based on the number of participants in the analysis set unless otherwise indicated.
- Categorical variables will be summarized using counts (n) and percentages (%) and will be presented in the form of n (%).
- Percentages will be reported to 1 decimal place.
- Continuous data will be summarized using the mean, standard deviation (SD), median, minimum, 25th and 75th percentiles, maximum, and number of participants with data.
- Means and medians will be reported at 1 more significant digit than the precision of the data. Standard deviations and confidence intervals will be reported at 2 more significant digits than the precision of the data. Quartiles, minima and maxima will be reported to the same level of precision as the original observations.
- The median will be reported as the average of the 2 middle numbers if the dataset contains even numbers.
- No preliminary rounding should be performed; rounding should only occur after analysis. To round, consider digit to right of last significant digit: if < 5 , then round down; if ≥ 5 , then round up.
- All p-values will be 1-sided and reported to 3 decimal places (e.g., 0.XXX). Values < 0.001 will be reported as < 0.001 .

If departures from these general conventions are present in the specific evaluations sections of this SAP, then those conventions will take precedence over these general conventions.

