At the interim analysis when approximately 50% of the participants have completed the study, a sample size re-estimation step will occur using the promising zone approach (Mehta and Pocock, 2011) and method of Chen, DeMets and Lan, based on the observed effect size at this interim analysis. The promising zone is defined as a conditional power of between 50% and 80%. If the conditional power falls into this region the sample size may be increased to raise the conditional power to 80%.

CONFIDENTIAL

Statistical Analysis Plan [Version 3.0]

The study will not stop enrolment awaiting these DMC reviews, though the DMC may recommend temporary or permanent cessation of enrolment based on their safety reviews.

A separate unblinded statistical team will prepare the above information for the DMC to review and make recommendations to the Sponsor. The following efficacy endpoints will be summarized at each interim analysis using the FAS:

Objectives	Endpoints
Primary	

 To evaluate clinical benefit of BLD-2660 in hospitalized adults with recently diagnosed SARS-CoV-2 infection 	
 Time to recovery as defined by no longer requiring oxygen support or hospital discharge, whichever occurs first

 To evaluate improvement in oxygenation in hospitalized adults with COVID-19 treated with BLD-2660 	
 Change from baseline to Day 10 or hospital discharge, if sooner, in the ratio of peripheral hemoglobin oxygen saturation to fraction of inspired oxygen (SpO₂/FiO₂)
Secondary	

 	

 Additional efficacy outcomes 	
 Time to hospital discharge readiness
Exploratory	

 Other efficacy outcomes 	
 Proportion of participants who require mechanical ventilation after study entry

6. References

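### The exploratory ventilation endpoint has no rule for death, so a patient who dies unventilated counts the same as one who recovered; the device and the observation window are also left open

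*SAP*

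**What the plan says.** SAP 5.7 names the endpoint "Proportion of participants requiring mechanical ventilation after study entry" and gives this derivation: "The frequency and proportion of participants will be reported by treatment group". The population is set by "The following exploratory endpoints will be analyzed using the FAS without adjustment for multiplicity" and the denominator by SAP 5.1: "Percentages will be based on the number of participants in the analysis set unless otherwise indicated". The arms are compared by a stratified CMH test, and "The common risk difference and two-sided 95% stratified Newcombe confidence interval will be reported".

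SAP 5.7 gives no rule for death or withdrawal, no last day of observation and no definition of the device. SAP 5.3.1 says missing-data rules stand with each endpoint's description; here there is none.

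On the device, Protocol 8.1.2 lists an item that begins "Non-invasive mechanical ventilation (via mask" and, separately, ventilation by endotracheal or tracheostomy tube or ECMO. Protocol Table 5 puts non-invasive ventilation at score 4. Its score 5 is "Hospitalized, on invasive mechanical ventilation or ECMO", and death is score 6. The endpoint carries neither qualifier.

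SAP 5.10 includes "Proportion of participants who require mechanical ventilation after study entry" among the four efficacy endpoints listed for interim summaries. Mortality over 28 days is a secondary endpoint in Protocol Section 3 but is not in the SAP 1.1 table.

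**The concern.** A proportion ventilated is read as a measure of deterioration: lower looks better. Death without ventilation removes a patient from any later chance of the event while leaving that patient in the denominator. An arm with more such deaths can therefore show less ventilation.

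The SAP deals with death elsewhere. Time to clinical improvement and time to discharge readiness both censor deaths at Day 28, which keeps those patients as never improved. The ventilation endpoint has no counterpart.

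The gap matters more in an interim summary than in the final report. Of the four listed efficacy endpoints, two censor death at Day 28, where it looks the same as a survivor still on oxygen or not ready for discharge. The SpO2/FiO2 endpoint leaves missing values missing at random, and the fourth is ventilation itself. None counts death as an event.

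Without a device definition, one dataset supports two different rates. Without an end day, a summary taken after the last patient's Day 10, as SAP 5.10 plans for the sponsor, would mix follow-up of about 10 to 28 days.

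**Working it through.** The documents state no expected rate, power or sample size for this endpoint, so there is no figure of the plan to reproduce. The check is arithmetic on the definition.

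**Inputs from the documents.** Arms of 80 and 40 (SAP 1.2). Background fatality among hospitalized patients of 14%, 95% CI 6.2 to 21.5% (Protocol 2.2).

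**Assumed, because the documents do not give them.** The rate of ventilation or death, the share of deaths that are unventilated, and the share of patients with mask support only.

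**Identity.** In each arm, P(ventilation or death) = P(ventilated) + P(died, never ventilated). For active minus control:

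D(ventilated) = D(ventilation or death) − [uA/80 − uC/40],

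where uA and uC are the numbers of unventilated deaths. One such death moves the active rate by 1/80 = 1.25 points and the control rate by 1/40 = 2.5 points.

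**Scale of deaths.** 0.14 × 80 = 11.2 active and 0.14 × 40 = 5.6 control. Over the quoted interval, 0.062 × 120 = 7.4 to 0.215 × 120 = 25.8 in all.

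**Equal shares create no difference.** If 30 to 50% of deaths are unventilated in both arms (assumed), that is 3.4 to 5.6 active and 1.7 to 2.8 control patients. This is 0.14 × 0.30 = 4.2% to 0.14 × 0.50 = 7.0% of each arm. The bracket is zero: both rates fall by about the same number of points and the difference is unchanged. Bias needs an imbalance.

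**Imbalanced illustrations.** Control has 8 of 40 ventilated and no unventilated deaths throughout. Differences are in points, with unstratified Newcombe 95% intervals for scale; the SAP plans a stratified interval.

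| Active: ventilated | Active: died unventilated | Ventilation alone | Ventilation or death |
|---|---|---|---|
| 16/80 | 0 | 0 (−16.5 to +13.8) | 0 (−16.5 to +13.8) |
| 12/80 | 4 | −5 (−21.0 to +8.4) | 0 (−16.5 to +13.8) |
| 8/80 | 8 | −10 (−25.5 to +2.8) | 0 (−16.5 to +13.8) |
| 12/80 | 8 | −5 (−21.0 to +8.4) | +5 (−11.9 to +19.1) |

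Row 3: 8/80 − 8/40 = 10% − 20% = −10, while (8 + 8)/80 − 8/40 = 0. Row 4 is the wrong-direction case: ventilation alone reads 15% − 20% = −5, while ventilation or death reads 20/80 − 8/40 = +5. Eight unventilated deaths in the active arm and none in control is a demanding assumption against about 11 and 6 deaths expected in all. The intervals are wide in every row.

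**Device.** If 5 to 15% of patients have mask support only (assumed), the definition moves 4 to 12 active and 2 to 6 control patients in or out of the numerator. That shifts each arm's rate by 5 to 15 points. It shifts the difference only if mask use differs between arms.

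**The case against.** The strongest reply is that death is not hidden. SAP 5.6.2 keeps the 6-point ordinal scale as a secondary endpoint, compared at Days 10/EOT, 14, 21 and 28 with death as score 6. Protocol 8.3.6 records every death in the eCRF, and survival status is collected at Days 14, 21 and 28. The ventilation endpoint is exploratory and unpowered, and the SAP nowhere labels its non-events as successes. The 14% figure may also not apply to a trial that excludes patients needing, or expected to need, mechanical ventilation. All of this stands, and it limits the consequence. It does not correct the ventilation risk difference, and the ordinal scale is not on the interim list.

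The separate table specifications mentioned in SAP Section 1, not available here, might settle the definition. SAP 5.3.1, however, places missing-data rules with the endpoint's description.

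Four stronger readings are tempting and are not supported:

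- *This is the only deterioration endpoint left in the SAP.* It is not; the ordinal scale remains.
- *Sites would count mask patients differently.* Protocol 8.1.2 has mask and tube support assessed as separate items, so the ambiguity lies in how the endpoint is derived from them.
- *Patients on mask support at entry would be counted as events.* That needs mechanical ventilation to include masks in the endpoint but exclude them in exclusion criterion 9.
- *A change would alter the DMC's risk/benefit review.* SAP 5.10 reports that review as already held.

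**Conclusion.** The point holds in a limited form. As written, the endpoint treats an unventilated death as a non-event, and its risk difference is offset by exactly the between-arm difference in unventilated deaths. With 8 of 80 against 0 of 40, the offset is 10 points. With equal percentages in the two arms it is zero. Which of these applies cannot be told from the documents, so the figures show what could happen and are not an estimate of bias. It would also be wrong to infer that the SAP rewards death by design; the effect follows from its silence together with the whole-set denominator.

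The missing device definition and end day are plain gaps in the text and rest on no assumption. Because the endpoint is exploratory and death is scored elsewhere, this is a worthwhile, inexpensive improvement. It does not threaten the trial's primary conclusions.

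**What to change.** In SAP 5.7, and in any remaining interim summary that reports this endpoint:

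- Analyse invasive mechanical ventilation/ECMO or death (Table 5 score 5 or 6) at any time from first dose through Day 28.
- State that score 4, which includes mask ventilation, is not an event.
- Beneath the composite, report ventilation and death separately by arm. The composite count minus the ventilation count gives the unventilated deaths.
- Say how patients who withdraw before Day 28 are counted.

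The cost is SAP wording and a small derivation. Type of support, ordinal score and survival status are already collected. SAP Section 1 calls for a protocol amendment when primary endpoints or analyses change, and this is neither. The small downside is that the headline rate is no longer a pure ventilation rate, but the component row keeps it.

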1.2. Schedule of Activities (SoA)

Table 2: Schedule of Activities

General Notes:

- In case of natural disasters or pandemics, some visits/study procedures can be done via virtual visits (e.g., telemedicine or telephone) or at home visits after hospital discharge. Refer to study reference manual for more details.
- Assessments completed as part of standard of care within the protocol defined windows, will not need to be repeated specifically for the protocol.

Procedure	Screening	Treatment Period			Follow-up			Post-study visit	Notes
		BL	Daily visits [‡]	EOT/ET*			EOS		
Study Day	-3 to -1	1	2-9	10	14	21	28	+60 days from EOS	Baseline (BL); End of Treatment (EOT), Early termination (ET); End of study (EOS) [‡] If a subject is discharged prior to Day 10, they will complete Day 5 and Day 10 visits assessments * This visit will be conducted at hospital discharge, if subject is discharged prior to Day 10
Visit window (days)				±1	±2	±2	±2	±10	
Informed consent	X								
Inclusion and exclusion criteria	X	X							
Demography	X								
Medical history	X								
Current medical conditions	X	X							Including time from onset of symptoms (fever, cough, etc.) to study entry, COVID-19 severity for each subject
Comprehensive physical exam	X			X					
Height and weight	X			X*					*Weight only

Procedure	Screening	Treatment Period			Follow-up			Post-study visit	Notes
		BL	Daily visits [‡]	EOT/ET*			EOS		
Study Day	-3 to -1	1	2-9	10	14	21	28	+60 days from EOS	Baseline (BL); End of Treatment (EOT), Early termination (ET); End of study (EOS) ‡ If a subject is discharged prior to Day 10, they will complete Day 5 and Day 10 visits assessments * This visit will be conducted at hospital discharge, if subject is discharged prior to Day 10
Visit window (days)				±1	±2	±2	±2	±10	
Limited physical exam		X	Day 5		X	X	X		Physical exam will be symptom-directed exam
Hematology	X	X	Day 5	X	X	X	X		Refer to Section 10.2
Clinical chemistries	X	X	Day 5	X	X	X	X		Refer to Section 10.2
INR	X						X		International normal ratio (INR)
Urinalysis	X						X		Refer to Section 10.2
Sputum samples and nasopharyngeal swab for SARS-CoV-2 PCR		X	Day 5	X	X	X	X		Samples to be frozen as specified in the laboratory manual for viral quantification.
Serum hsCRP and ferritin		X	Day 5	X	X	X	X		High sensitivity c-reactive protein (CRP)
Reserve blood sample for biomarker analyses		X	Day 5	X	X	X	X		Date and times to be recorded when samples were collected.
IL-6		X	X	X	X	X	X		Interleukin 6 (IL-6)

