2.2. Background

SARS-CoV-2, a positive-sense single-stranded RNA virus of zoonotic origin, is highly contagious in humans and is the cause of the ongoing worldwide pandemic of COVID-19. As of April 4, 2020, the SARS-CoV-2 has been responsible for more than 1.2 million infections and 70,000 deaths worldwide (data from <https://coronavirus.jhu.edu/>).

SARS-CoV-2 is transmitted via respiratory droplets (fomites infectious particles) within a range of about 2 meters and direct contact with contaminated surfaces. The median incubation period was estimated to be 4-5 days, and the majority (97.5%) developed symptoms within 11.5 days (CI, 8.2 to 15.6 days) of infection (Guan, 2020; Lauer, 2020). Higher viral loads are detected soon after symptom onset, with higher viral loads detected in the nose than in the throat (Zou, 2020). The mean viral load of severe cases was around 60 times higher than that of mild cases, suggesting that higher viral loads might be associated with severe clinical outcomes (Liu, 2020).

Clinical symptoms of COVID-19 include fever, cough, and dyspnea (Guan, 2020; Jiang, 2020; Rodriguez-Morales, 2020; Rothan, 2020); a small population of patients also may suffer from gastrointestinal symptoms (Guan, 2020; Guo, 2020). Radiologic features in the lungs include bilateral ground glass opacities on chest x-ray or computed tomography (CT) (Guan, 2020). COVID-19 appears to be more prevalent in males than females (Adhikari, 2020). The population most at risk are immune-compromised patients such as the elderly, and subjects with co-morbid diseases (e.g., diabetes, cardiovascular, cancer). This population is prone to serious outcomes, which may be associated with acute respiratory distress syndrome (ARDS) and cytokine storm (Adhikari, 2020; Guo, 2020). Approximately 14% (95%CI 6.2–21.5%) of hospitalized patients had fatal outcomes (case fatality rate, CFR) (Rodriguez-Morales, 2020).

Initially, the SARS-CoV-2 predominantly infects lower airways and binds to ACE-2 on alveolar epithelial cells (Guo, 2020; Kuba, 2010). It is a potent inducer of inflammatory cytokines. The “cytokine storm” or “cytokine cascade” is the postulated mechanism for organ damage. The virus activates immune cells and induces the secretion of inflammatory cytokines and chemokines into pulmonary vascular endothelial cells (Jiang, 2020).

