8.1.6. Antiviral Activity

Quantitative viral load using nasopharyngeal swab/sputum SARS-CoV-2 PCR will be used to monitor disease status during the study. For more details refer to the laboratory manual.

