10.2. Appendix 2: Clinical Laboratory Tests

- The clinical laboratory tests detailed in [Table 8](#) will be performed by a local laboratory, except where specified below, at the timing/frequency detailed in the SoA.
- Protocol-specific requirements for inclusion or exclusion of subjects are detailed in [Section 5](#) of the protocol.
- Additional tests may be performed at any time during the study as determined necessary by the Investigator or required by local regulations
- Investigators must document their review of each laboratory safety report.

Table 8: Protocol-Required Laboratory Assessments

Hematology	
White blood cell count (WBC) with absolute differential (Neutrophils, Lymphocytes, Monocytes, Eosinophils, Basophils) Hemoglobin Platelet count	Red blood cell (RBC) with indices (mean corpuscular volume [MCV] and mean corpuscular hemoglobin [MCH]) Hematocrit
Clinical Chemistries	
Alanine aminotransferase (ALT) Alkaline phosphatase Total and direct bilirubin (fractionated) Albumin Calcium Sodium Glucose Chloride	Aspartate aminotransferase (AST) Gamma-glutamyl transferase (GGT) Blood urea nitrogen (BUN) L-lactate dehydrogenase (LDH) Creatinine Potassium Total protein Bicarbonate
Urinalysis	
Basic Urinalysis (dipstick, including macroscopic appearance, bilirubin, blood, color, glucose, ketones, leukocyte esterase, nitrite, pH, protein, specific gravity, urobilinogen)	
Other Laboratory Assessments	

 • Troponin (serum) • IL-6 (to be analyzed at central laboratory) • D-dimer • Coagulation panel: International normalized ratio (INR) • Serum ferritin • Serum high sensitivity C-reactive protein (hsCRP) • Serum pregnancy test • SARS-COV-2 (COVID-19) test (RT-PCR via nasopharyngeal swab) 	

10.3. Appendix 3: Adverse Events: Definitions and Procedures for Recording, Evaluating, Follow-up, and Reporting

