5.2. Visit Windows

The following table outlines the analysis visits that data will be mapped to for analysis of efficacy, safety and pharmacodynamics data collected during the study. If after mapping, multiple data points share the same analysis visit, the data point closest to the expected study visit will be used. If there is a tie, the earlier of the visits will be used.

Study Visit	Analysis Visit	Analysis Window
Screening	Screening	0
Baseline	Baseline	0
Days 1 – 9	Days 1 – 9	0

Day 10	Day 10	± 1 day
Day 14	Day 14	± 2 day
Day 21	Day 21	± 3 day
Day 28/EOS	Day 28	± 3 day
Post Study Visit	Day 88	± 10 day

If Baseline is missing then screening data should be mapped to baseline for analysis purposes.

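### SAP 5.7 lets a normality check decide whether viral load is analysed raw or on the log scale, and does not say which specimen the values come from

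*SAP*

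**What the plan says.** **Scale.** SAP 5.7 derives the change by subtracting the baseline viral load from each later value and analyses it with the MMRM used for the SpO2/FiO2 endpoint. It then says: "The data may be log transformed prior to analysis if the assumptions of normality are violated". It gives no test, threshold or log base, and does not say whether the check is made blind to treatment. Values below the limit of quantification are replaced by half the limit, and only participants who are PCR-positive at baseline are analysed.

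**Specimen.** One row of the protocol's Schedule of Activities reads "Sputum samples and nasopharyngeal swab for SARS-CoV-2 PCR". It is marked at baseline and Days 5, 10, 14, 21 and 28, with the note "Samples to be frozen as specified in the laboratory manual for viral quantification". Protocol 8.1.6 states: "Quantitative viral load using nasopharyngeal swab/sputum SARS-CoV-2 PCR will be used to monitor disease status during the study". The laboratory table in protocol Appendix 2 has only "SARS-COV-2 (COVID-19) test (RT-PCR via nasopharyngeal swab" (the closing bracket follows) and no sputum test. SAP 5.7 names no specimen.

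**Several values at one visit.** The mapping rule in SAP 5.2 covers "analysis of efficacy, safety and pharmacodynamics data collected during the study". Where several values fall in one analysis visit, "the data point closest to the expected study visit will be used", and a tie goes to the earlier visit. Specimen type is not a criterion.

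**The concern.** There are two separate gaps.

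The first is the scale. Raw is the default, and the switch to logs is permitted rather than required, on a check with no stated rule. Two analysts with the same data could report different results and both comply with the SAP. On the raw scale the mean change mostly describes the participants with the highest loads.

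The second is the specimen. Two types are scheduled, one variable is analysed, and nothing requires baseline and follow-up to come from the same type. A change could therefore contain a specimen difference that has nothing to do with treatment or time.

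Only the second gap allows subtraction across specimens. The first makes any such mixture larger and harder to read.

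Antiviral activity is in the trial's title. Of the protocol's three virology endpoints (virus-free by Day 10, time to eradication, change in load), SAP 1.1 keeps only the change in load.

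**Working it through.** The documents give no SD, effect size or power for viral load, so there is no planned figure to reproduce. The inputs below are assumptions unless a source is named.

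**1. Why raw means follow the highest loads.** Protocol 2.2 reports mean load about 60 times higher in severe than in mild cases. Take two participants with baselines L and 60L, each with a 90% fall:
- raw changes: −0.9L and −54L, a ratio of 60;
- log10 changes: −1 and −1.

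The order of steps also matters. Viral load can be logged before subtraction, but a negative change cannot be logged afterwards.

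**2. Effect of scale on power.** The simulation used 3,000 runs with 80 active (the planned arm size) and 40 control. Baseline log10 load had mean 6 and SD 1. The mean fall was 2 log10, with a further 0.8 log10 on active and an SD of change of 1.5 log10. The comparison was baseline-adjusted, two-sided at about 5%, with a single specimen type.

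| Scale | Power | Rejection rate with no effect |
|---|---|---|
| log10 | 0.767 | 0.045 |
| raw | 0.137 | 0.026 |

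The Monte Carlo error on 0.767 is √(0.767 × 0.233 / 3000) ≈ 0.008. The model assumes a multiplicative effect, which favours logs. It ignores values below the quantification limit and treats all 120 participants as PCR-positive at baseline.

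**3. What a mismatched pair does.** Suppose there is no true change and the specimens differ by a factor k:

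| k | Apparent log10 change (either sign) | Apparent raw change from 1 million |
|---|---|---|
| 2 | 0.30 | −0.50 or +1 million |
| 10 | 1.00 | −0.90 or +9 million |
| 60 | 1.78 | −0.98 or +59 million |

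The documents give no sputum-versus-swab figure. The factor of 60 is borrowed from the severity comparison only to set an upper end.

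**4. Precision lost on log10.** If a fraction p of participants are mismatched, equally in both directions, with offset d, then SD(mixed) = √(SD² + p·d²). Power for a 0.8 log10 difference is Φ(0.8 / [SD × √(1/40 + 1/80)] − 1.96).

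With SD 1.5, d = 1.0 and p = 0.3, the SD is √(2.25 + 0.30) = 1.60 and the standard error is 1.597 × 0.1936 = 0.309. Power is then Φ(2.587 − 1.96) = 0.735. Without mixing it is 0.786.

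| Offset d (log10) | p = 0.1 | p = 0.3 | p = 0.5 |
|---|---|---|---|
| 0.30 | 0.785 | 0.782 | 0.778 |
| 1.00 | 0.769 | 0.735 | 0.702 |
| 1.78 | 0.732 | 0.637 | 0.560 |

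With SD 1.0 the unmixed power is 0.985, and the same grid runs from 0.984 down to 0.729.

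**5. Bias.** Simulated log10 power at p = 0.3 was 0.727 (d = 1.0) and 0.631 (d = 1.78), in line with the table. The rejection rate with no effect was 0.052 and 0.054. Mixing that is balanced between arms costs precision and leaves the false-positive rate near 5%.

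**The case against.** The strongest reply is that this is an exploratory endpoint with no multiplicity control, that any competent analyst would log viral loads, and that the specimen may be settled elsewhere. Protocol 8.1.6 refers to a laboratory manual, the SAP introduction places table specifications and example code in a separate document, and Appendix 2 lists only the swab. The slash in 8.1.6 may also mean one or the other. Much of this stands, and it limits the point to a minor one. It does not close the gaps: SAP 5.7 refers to neither outside document for specimen choice, a reading of one or the other still allows the type to change between visits, and the permissive log rule is in the SAP itself.

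The sizes are also assumed, and 50% mismatch is near the worst case when both specimens are scheduled at every visit. Baseline adjustment softens the loss. Take a change SD of 1.5, an assumed baseline to follow-up correlation of 0.5, and specimen type chosen at random at each visit. Offsets of 0.5, 1.0 and 1.5 log10 then inflate residual variance by about 5%, 18% and 40%, against 6%, 22% and 50% for an unadjusted change.

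A reader might infer four stronger things that the documents do not support:
- *SAP 5.2 selects the specimen by date.* It is a visit rule. Both specimens are scheduled for the same visits, and the windows for baseline and Day 5 are zero, so two specimens from one visit are left unresolved. Only from Day 10 on (windows of ±1 to ±3 days), and only if the two were taken on different days, could the rule choose between them.
- *Handling of values below the limit is also left open.* Half-limit substitution is prespecified and is not part of the error.
- *The protocol shows that sputum and swab differ.* Its background says "with higher viral loads detected in the nose than in the throat". No throat sample is scheduled, so this is only indirect evidence that sampling site matters.
- *Mixing biases the treatment comparison.* That would need the specimen mix to differ by arm, and nothing in the documents indicates that it would.

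**Conclusion.** The point holds as a minor one. SAP 5.7 leaves the scale of its only virology endpoint to an optional step after a normality check with no criterion. It also neither names a specimen nor requires baseline and follow-up to match, while the protocol schedules two types and its Appendix 2 lists one. Subtraction across specimens is not prevented, but whether it would happen cannot be established from the documents.

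The scale is the larger issue on the assumed inputs: power of 0.77 on log10 against 0.14 raw. Specimen mixing mainly costs precision, from almost nothing (0.786 to 0.785) to a substantial loss (0.786 to 0.560) at SD 1.5, depending on the assumed offset and mismatch rate. The endpoint is exploratory, and neither primary endpoint nor the primary conclusions are affected.

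**What to change.** In SAP 5.7, before the viral-load data are examined:
- make log10 viral load, taken before subtraction, the analysis variable, and delete the conditional transformation;
- name one analysis specimen (the swab would match protocol Appendix 2) and require that type at both baseline and follow-up;
- define baseline PCR positivity and the limit of quantification for that specimen;
- summarise the other specimen separately.

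The Schedule of Activities, protocol 8.1.6 and Appendix 2 should be reconciled on which specimens are tested. Half-limit substitution can stay.

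The cost is SAP wording and one extra table, with no new data. The downside is that participants without the named specimen at baseline leave that model.
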